1.7 Sponsor Details: Sheffield Teaching Hospitals NHS Foundation Trust
[name]
[contact]
[contact]

Protocol Signature Page

Role	Name	Signature
Principal Investigator	[name]
Co-Investigator	[name]
Co-Investigator	[name]
Co-Investigator	[name]
Co-Investigator	[name]
Co-Investigator	[name]
Co-Investigator	[name]
Co-Investigator	[name]

Principal Investigator Signature:

I confirm that I have read and understood protocol (Version Dated). I agree to comply with the study protocol, research governance, clinical trial regulations and appropriate reporting requirements.

Signature:

Date:

Print Name:

2 Scientific Summary

Background

Motor neurone disease (MND) is a neurodegenerative illness which causes progressive paralysis of muscles leading to death usually within 3 years of diagnosis. Dysphagia is a common problem in patients with MND, and causes difficulties in maintaining a safe and adequate oral intake of food and fluids. Gastrostomy feeding tubes are commonly used to support patients with dysphagia. The current practice of gastrostomy feeding is largely based on consensus and expert opinion rather than the outcomes of appropriately designed trials. There is lack of evidence to indicate the optimal timing for gastrostomy or which method of gastrostomy insertion is most appropriate. Additionally high quality evidence regarding survival and quality of life following gastrostomy insertion is lacking.

Aims

- i) Identify the current practice with regard to gastrostomy insertion in MND Care Centres within the UK and compare it with the practice in the Sheffield and Leeds MND Care & Research Centres.
- ii) Identify the most appropriate method for gastrostomy insertion in patients with MND.
- iii) Identify the optimal timing for gastrostomy use in patients with MND.
- iv) Compare outcomes between different gastrostomy protocols within and between centres with regard to (a) survival; (b) complications; (c) change in weight; (d) change in quality of life; and (e) carer burden, post gastrostomy.
- v) Develop guidelines for gastrostomy use in patients with MND.

Plan of Investigation

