This form will be completed at the end of the gastrostomy procedure, either by the local champion or the member of the team performing the gastrostomy insertion. The form is designed to capture the details of the procedure with regard to staffing; gastrostomy equipment; drugs given; patient monitoring and respiratory support; as well as, any complications that occur during the procedure.

iv) 3-month Follow Up Patient Evaluation Form (see Appendix 4)

This form is designed to capture data with regard to gastrostomy complications occurred prior to patient's hospital discharge and those occurred after the hospital discharge up to the 3-month patient evaluation. Weight and ALSFRS-R for each patient will also be recorded. This form will be completed by the local champion after a patient's usual follow up visit which coincides nearest with 3 months post gastrostomy.

v) 12-month Follow Up Patient Evaluation Form (see Appendix 5)

This form is designed to capture data with regard to gastrostomy complications occurred in the period of time between the 3-month patient evaluation and the 12-month patient evaluation. Weight and ALSFRS-R for each patient will also be recorded. This form will be completed by the local champion after a patient's usual follow up visit which coincides nearest with 12 months post gastrostomy.

vi) McGill Quality of Life Questionnaire (MQOL) (see Appendix 7)

This is a well-established questionnaire, designed in the context of palliative care, to identify the health-related quality of life of patients with a terminal illness. It balances physical and non-physical aspects of quality of life, and includes both positive and negative influences on quality of life [53]. This questionnaire will be completed by patients at baseline and at 3 months post gastrostomy.

vii) Modified Caregiver Strain Index (MCSI) (see Appendix 8)

This is a well-established questionnaire, designed to identify the strain levels among informal carers of patients with long-term illness. It will be used in this study to assess the quality of life of the main carer of the patient and the impact that the treatment is having on the carer [54]. It will be completed by carers at baseline and at 3 months post gastrostomy.

viii) Gastrostomy-specific questionnaire (Gastro-Qu) (see Appendix 9)

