7.5 Study Outcomes

Primary:

- i) *Difference in the mortality rate in the first month following gastrostomy in PEG and PIG/RIG patients.*

Secondary:

- i) *Difference in the complication rate (classified in groups according to seriousness and time of occurrence) following gastrostomy in PEG and PIG/RIG patients.*
- ii) *Median survival time from (a) placement of feeding tube, (b) symptom onset, and (c) time of diagnosis of the disease in PEG and PIG/RIG patients.*
- iii) *Nutritional status changes (weight and BMI) following gastrostomy in PEG and PIG/RIG patients.*
- iv) *Self-perceived quality of life changes (measured by MQOL, gastrostomy questionnaire and qualitative interviews) following gastrostomy in PEG and PIG/RIG patients.*
- v) *Change in carer quality of life as measured by MCSI and qualitative interviews.*

Analysis will also include looking into how factors, such as (a) respiratory status, (b) site of symptoms onset, and (c) stage of disease, influence safety and survival following gastrostomy in PEG and PIG/RIG patients.

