7.7 Data Analysis

Quantitative data analysis

All quantitative data will be managed and analysed using SPSS for Windows version 14.0 (SPSS Inc., 1998). Exploratory data analysis will be initially carried out to establish the distribution of all continuous and categorical variables. Descriptive statistics (means, standard deviations, percentages) will be used to describe the characteristics of the participating centres, the participants and all the main variables of the study. Non-parametric tests (Spearman rank correlation tests and Mann Whitney U tests) will be performed for non-normally distributed continuous variables. Cronbach's alpha (α) coefficients will be determined for the measures that will be used in the study (i.e., MQOL, MCSI, gastrostomy questionnaire) in order to establish their internal consistency.

Continuity corrected Chi-square (χ^2) tests will be performed to determine the difference in the first-month mortality rate and the complication rate following gastrostomy in PEG and PIG/RIG patients. The same tests will be also performed to determine the self-perceived quality of life changes following gastrostomy in PEG and PIG/RIG patients as well as to determine the changes in carer quality of life. Kaplan-Meier survival curves will be used to determine the median survival time from placement of feeding tube, symptom onset and time of diagnosis of the disease in PEG and PIG/RIG patients. Independent samples t-tests will be used to determine the nutritional status changes following gastrostomy in PEG and PIG/RIG patients. Predictors of survival (e.g., respiratory status, site of symptom onset, stage of disease) following gastrostomy will be determined using logistic regression analysis and Cox proportional hazards regressions analysis.

Qualitative data analysis

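### The protocol promises to compare carer burden between gastrostomy methods, but neither the carer outcome nor its analysis names the PEG and PIG/RIG groups

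*Protocol*

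**What the plan says.** **The aim.** Section 2, Scientific Summary, Aims (iv), sets out to "Compare outcomes between different gastrostomy protocols within and between centres with regard to" a list of five outcomes, the last of which is "e) carer burden, post gastrostomy".

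**The outcome.** Section 7.5, secondary outcome v, reads in full: "Change in carer quality of life as measured by MCSI and qualitative interviews". The primary outcome and secondary outcomes i to iv all end by naming the two method groups. Outcome iii is typical: "Nutritional status changes (weight and BMI) following gastrostomy in PEG and PIG/RIG patients".

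**The analysis.** Section 7.7 introduces continuity-corrected chi-square tests as a between-method comparison: these "tests will be performed to determine the difference in the first-month mortality rate and the complication rate following gastrostomy in PEG and PIG/RIG patients". It then applies the same tests to patient quality of life, with both groups named, "as well as to determine the changes in carer quality of life", with no groups named.

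**The instrument.** Section 7.2 A(vii) says of the MCSI: "It will be completed by carers at baseline and at 3 months post gastrostomy". It also says the index will be used to assess the carer's quality of life and "the impact that the treatment is having on the carer".

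**The concern.** The stated question is whether carer burden differs by method of insertion. An analyst who follows outcome v and the carer clause of 7.7 to the letter is not told to compare methods. What can be done literally is to describe a change from baseline to 3 months.

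That change has a second weakness. Every patient is enrolled on a decision to refer for gastrostomy (7.4), so there is no comparator without it, and section 6 describes MND as progressive. A change in strain over three months therefore mixes any effect of the tube with further disease. The treatment-impact wording in 7.2 invites a reader to treat the mixture as a treatment effect. A rise in strain could be taken as harm from gastrostomy, or a real benefit could be hidden by progression. The study is meant to produce guidelines, so either misreading could reach practice.

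An outcome open to two readings also leaves the contrast to be chosen after the data are seen.

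**Working it through.** **Step 1. Set the texts side by side.**

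| Outcome | PEG and PIG/RIG named in 7.5? | Named in 7.7? |
|---|---|---|
| Primary: one-month mortality | Yes | Yes |
| i Complications | Yes | Yes |
| ii Median survival | Yes | Yes |
| iii Weight and BMI | Yes | Yes |
| iv Patient quality of life | Yes | Yes |
| v Carer quality of life (MCSI) | No | No |

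The omission is confined to the carer outcome and occurs in both places, while aim iv(e) asks for the comparison.

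**Step 2. Check whether other text supplies the contrast.** Section 4 (iv) says only that carers' quality of life and views will be assessed. Section 7.6 says disease course, nutritional and respiratory status are recorded and that their effect on primary and secondary outcomes will be examined, but it gives no carer model and no method groups for carers. The factor analyses at the end of 7.5 concern safety and survival, and the regressions in 7.7 concern survival.

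**Step 3. Check the test.** A chi-square test needs categories. The MCSI in Appendix 8 has 13 items, each with three response options, and the outcome is a change in its score. The test named does not use the baseline score as a covariate.

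**Step 4. Illustrate the size.** The protocol has no figure to reproduce here: it gives no MCSI standard deviation, target difference or completion rate. The inputs below are assumptions. The number of carers completing both forms is taken as 200 to 504, where 504 is the recruitment target and so an upper limit. Drift is in SDs of the change score, is shared by both methods, and there is no method effect.

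Probability that a before-and-after test is significant at two-sided 5% (the opposite tail is negligible except at the smallest drift, where it is still below 0.001):

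P ≈ Φ(drift × √n − 1.96)

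- Drift 0.2, n = 200: Φ(2.83 − 1.96) = Φ(0.87) = 0.81
- Drift 0.2, n = 300: 0.93; n = 400: 0.98
- Drift 0.2, n = 504: Φ(4.49 − 1.96) = Φ(2.53) = 0.99
- Drift 0.1, n = 200: Φ(1.41 − 1.96) = Φ(−0.55) = 0.29
- Drift 0.1, n = 504: Φ(2.24 − 1.96) = Φ(0.28) = 0.61

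A between-method contrast in change subtracts drift common to both groups, so under these assumptions its false-positive rate stays at 5%. That follows by construction.

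Power of that contrast for an assumed method difference of 0.3 SD of change, equal groups:

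Power ≈ Φ(0.3 × √(n/4) − 1.96)

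- n = 200: Φ(2.12 − 1.96) = 0.56
- n = 300: 0.74; n = 400: 0.85
- n = 504: Φ(3.37 − 1.96) = 0.92

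With a 2:1 split the range is 0.52 to 0.89. These figures treat carers as independent and ignore any centre effect.

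**The case against.** The strongest reply is that the comparison is already implied. The tests in 7.7 are introduced as comparisons of PEG with PIG/RIG, a chi-square test of that kind is for independent groups, and these are the only two groups defined in 7.5 to 7.7. Read with aim iv(e), a between-method comparison of carer change is at least as natural as a pooled one. The missing phrase ends in the word patients, which would not literally fit carers. This stands to the extent that the contrast is unspecified rather than excluded.

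A reader might go further and infer that the plan analyses carers as one pooled before-and-after group, and that it credits disease progression to the gastrostomy. The documents support neither. No passage prescribes a pooled, paired or before-versus-after test. The phrase in 7.2 describes what the instrument is used for and is not a rule of interpretation. Section 4 states no directional hypothesis for carers, and 7.6 promises to examine disease variables against the secondary outcomes.

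Two further points are also right. If strain does rise, rejecting no change is a correct result, and only a causal reading of it would be wrong. The lack of a group without gastrostomy limits the other change outcomes too, so it is not special to outcome v.

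What the reply does not remove is the mismatch between the aim and the outcome, repeated in 7.7. A full carer model could be left to a statistical analysis plan, but one written from outcome v would inherit the omission.

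**Conclusion.** The point holds as a mismatch between a stated aim and the outcome and analysis meant to serve it. Carer burden is to be compared between methods, yet the carer outcome is the only one with no method groups and is given only a chi-square test on a change in score. It concerns one secondary outcome and does not touch the primary analysis.

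The risk of misreading an overall change is real but conditional: it arises only if that change is reported as a treatment effect. The probabilities of 0.29 to 0.99 rest wholly on assumed drift and completion. They show what such a reading could produce and are not a demonstrated error rate of the plan.

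The between-method contrast answers aim iv(e) and removes drift common to both groups. It cannot isolate the effect of gastrostomy, because all patients are referred for one. Method is not randomised and, by 7.6, most centres use only one approach, so equal drift in the two groups is not assured.

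**What to change.** 1. **Section 7.5, outcome v.** Reword to: *Change in carer strain (MCSI) from baseline to 3 months in carers of PEG and PIG/RIG patients.* Keep the qualitative interviews as a separate descriptive component.
2. **Section 7.7.** Replace the chi-square test for carers with the between-method difference in 3-month MCSI score, adjusted for baseline MCSI and baseline ALSFRS-R, reported with a confidence interval. State that method is largely tied to centre, so the estimate is an adjusted observational contrast.
3. **Overall change.** Report the baseline to 3-month change across all carers as descriptive only, and amend 7.2 A(vii) so that it is not presented as the impact of treatment.

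**Cost.** Wording in three places and one regression. MCSI at both times, baseline ALSFRS-R and procedure type are already collected, so no new data, visits or participants are needed. The one loss is that the overall change can no longer be offered as an effect of gastrostomy, which the design could not support in any case.

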7.6 Statistical Power Analysis

There are few studies in the MND literature comparing survival time or one month post procedure mortality of patients with MND following different methods of gastrostomy. Three recent studies [24, 34, 47] reported that there was no significant difference in survival between PEG patients and RIG patients. These studies were retrospective, contained small numbers and were not adequately powered to detect potentially important clinical differences. One small prospective study [30] reported that there was a significant difference ($p = 0.004$) between survival in PEG patients and survival in RIG patients but this was in the subgroup of patients with respiratory failure. The median survival after gastrostomy was 140% higher in the RIG group compared to PEG group. Given the lack of comparative studies we have reviewed the literature for mortality data. For MND patients undergoing PEG the 30 day mortality rates range from 4% to 25% [19, 26, 30-32, 47-51]. For MND patients undergoing RIG procedures the 30 day mortality rate ranges from 4% to 9% [30, 35, 47].

Based on the review of the literature we hypothesise that a difference in one month mortality between PEG and PIG/RIG of between 0 % and 21% may exist. We aim to power PROGAS to detect a conservative, but clinically important, 30 day mortality rate difference of 8%. Power analysis calculations indicated that a minimum sample of 442 patients would be required to attain sufficient statistical power. For PROGAS, anticipating an 80% participant response rate over a 21-month recruitment period, we estimate that we will recruit 504 patients. This sample size will provide statistical power of 80% at a 5% level of statistical significance to detect a difference of 8% in mortality at one month, using a continuity corrected Chi-square (χ^2) test.

We aim to identify the most appropriate method of gastrostomy in terms of safety and patient experience. The study is designed to be easily carried out in a routine clinical setting and to assess in a pragmatic way current practice throughout the UK. It is clear that multiple variables at different sites may impact on the outcomes. However the key variables including MND disease course, nutritional and respiratory status, are being recorded and we will

interrogate the data for the effect of these parameters on the primary and secondary outcome measures. Patient and clinician choices will inevitably impact on the timing of gastrostomy but at most centres these will not have a major effect on the type of gastrostomy procedure undertaken. An initial evaluation of the participating centres has demonstrated that most centres perform either only PIG/RIG procedures or only PEG procedures, which will reduce the variability which could potentially be introduced by physicians selecting particular procedures.

The power analysis calculation and the plan for subsequent statistical analysis were facilitated by experienced statisticians at the Research and Development department of the Sheffield Teaching Hospitals NHS Foundation Trust and the Yorkshire and Humber NIHR Research Design Service.

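### Method is largely fixed by centre, but the primary test and the 80% power statement treat patients as independent; even modest clustering can break both

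*Protocol*

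**What the plan says.** Three statements in Protocol section 7.6 bear on this.

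- On how method is assigned: "most centres perform either only PIG/RIG procedures or only PEG procedures". Patient and clinician choices affect timing, but "at most centres these will not have a major effect on the type of gastrostomy procedure undertaken".
- On site influences: "It is clear that multiple variables at different sites may impact on the outcomes".
- On power: a minimum of 442 patients is needed, 504 are expected, and "This sample size will provide statistical power of 80% at a 5% level of statistical significance" for an 8-point difference in one-month mortality, using a continuity-corrected chi-square test.

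Section 7.7 names the same test for one-month mortality (the primary outcome in 7.5) and for complication rates. It gives respiratory status, site of onset and stage of disease as examples of survival predictors for logistic and Cox regression; centre is not named. Section 7.1 asks all centres to keep their usual gastrostomy practice. The protocol contains no ICC, design effect, centre term or cluster-robust variance.

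**The concern.** When most centres offer one method, the PEG v PIG/RIG contrast is made mainly between centres. Patients at one centre share staff, sedation practice, ventilatory support and aftercare, so their outcomes may be correlated. The chi-square test and the sample-size formula behind it both assume that they are not.

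Any positive correlation makes the difference between methods more variable than the test allows. The test then rejects a true null hypothesis more often than it would with independent patients, and 504 patients carry less information than 504 independent ones. The results are meant to support guidelines, so a false or fragile difference in mortality would matter.

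This is not a detail left to a later analysis plan. The protocol itself fixes the primary test and states the power.

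**Working it through.** **Inputs from the protocol.** Expected N 504 and minimum N 442; 8-point difference; 5% level; 80% power; continuity-corrected chi-square (7.6). Number of centres: 18 (7.4) or 15 committed (7.1). Literature ranges for 30-day mortality: 4% to 25% for PEG and 4% to 9% for RIG (7.6).

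**Assumptions.** Two-sided test, equal groups, equal centre sizes, the arm rates, and an ICC from 0 to 0.05. The protocol states none of these.

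**1. The plan's own figure.** Without arm rates, 442 cannot be reproduced uniquely. The usual two-proportion formula for independent patients comes close:

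- 5% v 13%: 450 with continuity correction.
- 6% v 14%: 440 without correction, 488 with it.
- Power at 504 with correction: 84.9% for 5% v 13%, 81.4% for 6% v 14%, 78.1% for 7% v 15%.

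The stated figures therefore fit a calculation with no allowance for clustering.

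**2. How much clustering the surplus absorbs.** If 442 is the N for 80% power, the margin is 504/442 = 1.14. The design effect is DE = 1 + (m − 1) × ICC.

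- 18 centres: m = 504/18 = 28, so ICC = 0.14/27 ≈ 0.005.
- 15 centres: m = 504/15 = 33.6, so ICC = 0.14/32.6 ≈ 0.004.

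**3. Power of an analysis that allows for clustering.** Effective N = 504/DE, with 18 single-method centres. Power is from exact binomial enumeration of the corrected chi-square at the effective N, which gives about one point more than the formula in step 1.

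| ICC | DE | Effective N | Power, 5% v 13% | Power, 6.5% v 14.5% |
|---|---|---|---|---|
| 0 | 1.00 | 504 | 86% | 81% |
| 0.005 | 1.14 | 444 | 81% | 75% |
| 0.01 | 1.27 | 397 | 76% | 70% |
| 0.02 | 1.54 | 327 | 66% | 60% |
| 0.05 | 2.35 | 214 | 43% | 39% |

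These figures make no allowance for the few centre-level degrees of freedom (about 16 with 18 centres) or for unequal centre sizes. Both would lower them. Centres that use both methods would raise them.

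**4. Type I error of the planned test.** Beta-binomial simulation, 18 centres of 28, 10% mortality in both groups, corrected chi-square on all 504 patients. The number of mixed centres is not given; 6 of 18, each split equally, is an illustration.

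| ICC | All centres single-method | 6 of 18 centres mixed |
|---|---|---|
| 0 | 3.6% | 3.4% |
| 0.005 | 4.7% | 4.2% |
| 0.01 | 6.0% | 5.1% |
| 0.02 | 8.8% | 7.0% |
| 0.05 | 16.7% | 12.3% |

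The starting value is below 5% because the continuity correction is conservative. That gives the planned test some slack before it exceeds its level.

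**The case against.** **The harm is conditional.** A reader might infer that the power is certainly overstated and that the test certainly fails its 5% level. The protocol does not support that, because it gives no ICC. At about 0.005 or below, the continuity correction keeps the type I error under 5% and the surplus over 442 roughly preserves the power. This stands. It also cuts the other way: the protocol offers no reason to assume so low a value, and it acknowledges site influences.

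**Most centres is not all centres.** Mixed centres contribute within-centre comparisons and reduce the inflation. This stands, and the second column in step 4 shows it. The problem shrinks but remains at an ICC of 0.02 and above.

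**The planned test would still reject often.** A reader might take the falling power figures as those of the planned chi-square. They are not. Under 5% v 13% with single-method centres, the unadjusted test on 504 patients rejects in about 83%, 81% and 77% of simulated trials at ICC 0.01, 0.02 and 0.05. Part of that comes from a test that rejects too readily, so it is not power at a true 5% level.

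**Single-method centres have a real advantage.** Section 7.6 says that they limit variability from clinicians choosing the procedure for individual patients. That is a legitimate point about selection, but it does not address variation between centres.

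**The analysis was expected to develop.** Section 7.1 says that the centre survey will refine the analysis plan. The aims mention comparisons within and between centres, and 7.6 promises to examine disease course, nutritional and respiratory status against the outcomes. None of this puts centre into the primary test or the power statement.

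**Intervals.** A reader might add that confidence intervals will be too narrow. The protocol plans none for the primary comparison, so this would apply only to an interval computed on the same independence assumption.

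**Conclusion.** The structural fault is clear from the text: exposure is largely set by centre, site influences are acknowledged, and both the primary test and the power statement ignore centre. Its size is not known. Under the assumptions above, an ICC above roughly 0.005 to 0.01 is enough for the planned test to exceed 5% and for a valid analysis to miss the stated 80%. With 6.5% v 14.5%, power is already about 75% at ICC 0.005. Below that range the plan may be adequate.

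It would be wrong to infer that allowing for clustering settles the comparison. It corrects the variance only. Where method and centre coincide, differences between centres in patient selection, ventilatory support, sedation or aftercare remain confounded with method, and no clustering adjustment separates them.

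**What to change.** **Section 7.7.** Analyse the primary outcome and the between-method secondary outcomes with allowance for centre. For mortality, use a logistic model with a random centre effect, or GEE or cluster-robust standard errors with a small-sample correction for 15 to 18 clusters. Fixed centre effects are unsuitable, because a single-method centre then contributes nothing to the method contrast.

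**Section 7.6.** State the assumed arm rates, the allocation between methods and the number of centres. Give power over a range of ICCs, for example 0 to 0.05, and qualify the 80% accordingly.

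**Limitation.** State that the adjustment does not remove confounding of method with other centre practices.

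**Cost.** Wording and analysis only. The centre is the first two digits of every participant code (section 8.1), so no new data are needed. The stated power becomes less favourable and p-values will tend to be larger.
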